A repeated A1c should be done 4 weeks after the first positive test for asymptomatic patients.

In symptomatic individual, a single positive test is sufficient.

Location of Research:

Location of Research	Expected number of subjects per site
Community Clinic Batu Berendam	56
Community Clinic Bukit Rambai	55
Community Clinic Sungai Udang	55

Recruitment pamphlets that contain general information of the study will be placed in all the healthcare clinics in Malacca. During the process of recruitment, a trained research assistant, clinical dietitian (one of the co-researchers) or family medicine specialist (one of the co-researchers) will inform potential prediabetic individuals of the study both verbally and will be provided written information (Appendix A). Newly diagnosed prediabetic individuals who are agreeable to participate will be provided written informed consent (Appendix A). Study visits (recruitment and follow-up visits) of this study will be determined based on the healthcare clinic appointment schedules. Those who decline to participate continue to receive their routine treatment as usual, and care provided to each prediabetic individual is not affected nor affected by each individual's decision to either participate or not participate in the study. An overview of the study procedure is illustrated in Figure 3. All the newly diagnosed prediabetic individuals who fulfill the inclusion criteria will be invited to participate in the present study. They will be recruited when they visit the diet clinic for the first time for their initial appointment scheduling. This would be considered the baseline visit. OGTT, HbA1c and FBS results will be traced from medical records.

Data regarding sociodemographic information and anthropometric measurements will be collected in the baseline visit. Enrolled participants will be interviewed by a trained

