The sample size is estimated using G*Power software version 3.1.9.4 (Erdfelder, Faul and Buchner, 1996). To determination of association between chrononutrition and glycemic control, the β -coefficient of 0.13 adopted from Sakai *et al.*, (2018), the power was set to 0.9 with 2 sided significance level and alpha error given 0.05, a total of 83 prediabetic adults expected in this study. To compensate for the non-responding and non-compliance during follow-up, a dropout rate of 50% will be considered, the total sample size required is 166 subjects in the study for 6 months.

Test Family: T Test

Statistical Test: Linear Multiple Regression Fixed Model, single regression coefficient

Tail(s): 2

Effect Size (β -coefficient): 0.13 (Sakai *et al.*, 2018)

α Error prob: 0.05

Power(1- β err prob): 0.90

[figure not shown]
Total Sample Size: 83 prediabetes individuals

50% dropout rate taken as consideration in study for 6 months follow up, total 166 prediabetes individuals shall be recruit in this study.

Dropout Rate:

$$= \frac{83}{1-0.5} = 166 \text{ prediabetic individuals}$$

Figure 3: Flow diagram of the study design

Participants will be undergoing OGTT, FBS and HbA1c tests after an overnight fast of 8-10 hours. This is a routine universal test for prediabetes/ diabetes diagnosis. Participants will be informed to eat their usual diet for three days prior to the test. The diagnostic value for diabetes on plasma glucose. the diagnostic values for prediabetes and diabetes based on OGTT, and the diagnostic values for prediabetes and diabetes based on HbA1c have been shown in Table 1, Table 2 and Table 3, respectively. Fasting blood sample will be taken for FBS and HbA1c tests. Subsequently, participants will be given 75-gram glucose water to drink within 5 minutes. Blood sample will be taken after 2 hours for glucose determination. Participants should rest throughout test with only plain water is allowed to drink. Figure 4 shows the procedure of OGTT. All the tests will be conducted in the healthcare clinic lab. Results will be traced from medical record.

Table 4: Summary of data collection and timeline

Data	Baseline	3 months	6 months
Sociodemographic			
Age	.	.	.
Date of Birth	.	.	.
Marital Status	.	.	.
Education Level	.	.	.
Occupation	.	.	.
Monthly Household Income	.	.	.
Health History	.	.	.
Smoking Habit	.	.	.
Supplementary Consumption	.	.	.
Anthropometry			
Weight	.	.	.
Height	.	.	.
Waist Circumference	.	.	.
Visceral Fat	.	.	.
Body Fat	.	.	.

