pattern from the validated questionnaires PSIQ and light exposure from the validated questionnaire HLEQ.

Statistical Analysis

All data will be performed statistical analysis using the SPSS software version 20 (SPSS Inc., Chicago, IL, USA). The socio-demographic will be presented as mean, standard deviations, median, interquartile range, frequency, and percentage. Data cleaning will be performed to exclude the outlier data before the normality is checked using Kolmogorov-Smirnov Test. The investigator considered $p < 0.05$ to be statistically significant. Chronotype, sleep quality, and light exposure will be analyzed as categorical variables whereas dietary intake, chrononutrition, anthropometry, glycemic measure, and physical activity will be analyzed as continuous variables.

The investigator will perform a multivariable generalized linear model to examine the association between night meal pattern (last night mealtime either dinner or supper with calories intake, frequency of night snacking, and the total number of the night snacking) and glycemic outcome (HbA1c, FPG, 2hPPG, CGM profile) by adjusting for the potential covariates. Specifically, nighttime will be characterized by the time range from 1900 and 0659 hours based on Malaysia solar time. The investigator will explore the late-night meal timing in 2000, 2100, and 2200 to examine its association with glycemic outcomes. The potential confounders include sociodemographic characteristics, physical activity, sleep pattern, sedentary behavior, diet quality, and light exposure will be controlled. ANCOVA test will be performed to understand the association between chrononutrition (breakfast skipping, meal frequency, eating window, sleep timing, chronotype, and fasting pattern) with glycemic variables, controlling for potential covariates (sociodemographic characteristics, light exposure, diet quality, physical activity and sleep pattern).

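### Clinic is not named in either covariate list, so residual differences between the three clinics could appear as meal-timing associations

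*Combined protocol and SAP*

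**What the plan says.** Section 3, Location of Research, names three community clinics. Under the column headed "Expected number of subjects per site" it gives 56, 55 and 55. Recruitment is by convenience sampling, and nothing balances participants across clinics. Dietitian and nurse-educator care is routine treatment that the study leaves unchanged (Section 1 and the visit description in Section 3). On the fasting glucose, OGTT and HbA1c measurements the plan says: "All the tests will be conducted in the healthcare clinic lab". Results are then traced from medical records.

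Under Statistical Analysis, the generalized linear model for night-meal pattern has this covariate statement: "The potential confounders include sociodemographic characteristics, physical activity, sleep pattern, sedentary behavior, diet quality, and light exposure will be controlled". The ANCOVA for chrononutrition lists sociodemographic characteristics, light exposure, diet quality, physical activity and sleep pattern. Neither list names clinic. The generalized linear model for lifestyle factors and the two logistic regressions have no covariate list.

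Clinic is not among the sociodemographic items in Table 4 or Appendix B, so that term does not bring it in. No stratified analysis, random effect, cluster-robust error or sensitivity analysis by clinic appears anywhere.

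**The concern.** The study is observational, so covariate adjustment is its main protection against confounding. Clinic is a natural candidate. The conceptual model in Section 1 places each person in a local environment of work schedules, community and routines that shape meal timing. Convenience sampling can give each clinic a different case mix. Usual care is not standardised by the study, and no central laboratory or cross-clinic calibration is stated.

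If clinics differ in meal timing and also in glycaemia, a model without clinic attributes part of the between-clinic difference to meal timing. A false association between late eating and poorer glycaemia would bear directly on the study's main hypothesis. Clinic should be known for every participant from enrolment, with less error than the self-reported covariates already listed.

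**Working it through.** **1. The plan's own figure.** Sample size Calculation specifies "Statistical Test: Linear Multiple Regression Fixed Model, single regression coefficient", with "Effect Size (β -coefficient): 0.13" and "the power was set to 0.9 with 2 sided significance level and alpha error given 0.05". For one coefficient, the noncentrality is √(f²·N) with N − p − 1 degrees of freedom, where p is the number of predictors. With f² = 0.13 and N = 83 this is √10.79 = 3.285, and power is 0.9007 at p = 1. The stated 83 is reproduced, provided 0.13 is entered as f². Then 83/(1 − 0.5) = 166 = 56 + 55 + 55. The check below uses N = 83 and does not dispute it.

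**2. How the bias arises.** The documents give no clinic differences, so they are assumed. Let the clinic means be −d, 0 and +d, in within-clinic SD units, in both meal timing and glycaemia, with equal clinics and no association within clinics. The between-clinic variance is (2/3)d² in each variable. Without clinic in the model the expected slope is (2/3)d² / [1 + (2/3)d²], which is also the share of variance lying between clinics:

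- d = 0.2: 0.0267/1.0267 = 0.026
- d = 0.3: 0.06/1.06 = 0.057
- d = 0.5: 0.1667/1.1667 = 0.143

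The simulation has no other covariates, so d must be read as the spread that remains after adjustment for those the plan lists.

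**3. Error rate.** Simulation at N = 83, normal errors, no true meal-timing effect, two-sided 5% test, 20,000 replicates:

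| Spread d | No clinic term, aligned | No clinic term, random clinic order | Clinic in model |
|---|---|---|---|
| 0.2 | 5.7% | 5.4% | about 5% |
| 0.3 | 8.3% | 6.3% | about 5% |
| 0.5 | 25.3% | 15.0% | about 5% |

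Aligned means that the clinics fall in the same order on both variables. This is the worst case.

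**4. Bounds.** If clinic accounts for 5% of the variance of glycaemia and none of meal timing, there is no bias and the error is 4.8%. If clinic effects on the two variables are drawn independently, with variance shares of 1% to 10%, the error without clinic is 4.5% to 7.3%. A larger retained sample makes the aligned case worse: at N = 120 the rates for d = 0.3 and 0.5 are 9.2% and 35%, and at N = 166 they are 11.5% and 46%.

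**5. Cost of adjustment.** Two clinic indicators move power at N = 83 from 0.9007 to 0.9005 (p from 1 to 3) or from 0.9003 to 0.9001 (p from 6 to 8). If clinic explains a share r of meal-timing variance, f² becomes 0.13(1 − r) and the noncentrality √[83 × 0.13 × (1 − r)]. With p = 3:

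- r = 2%: 3.252, power 0.895
- r = 5%: 3.202, power 0.885
- r = 10%: 3.116, power 0.868

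This leaves out any gain from lower residual variance in glycaemia.

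**The case against.** The premises are inferred. No section reports a clinic difference in meal timing, care, case mix or assay. A reader might infer that the clinics use different laboratories or counsel differently, but the documents do not say so. They refer to the clinic laboratory without saying how many there are. Section 1 describes routine care under one national guideline and says that the guideline contains no meal-timing advice. People already exposed to time-of-eating information are excluded. Counselling is therefore an unlikely source of clinic differences in the exposure. A constant laboratory offset would cancel in change scores, and the continuous glucose monitor is a single device type.

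Part of the pathway is also covered already. Education, job, income and ethnicity are plausible reasons for clinics to differ, and sociodemographic characteristics are in both lists.

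These points stand, and they limit the likely size. They do not remove the concern: bias needs residual differences in both variables, and local routines together with convenience sampling can produce them without any difference in laboratory or advice.

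A reader might also infer that clinic is left out of every model. That goes too far. The night-meal list is worded as what the confounders include, so it may not be exhaustive, and the lifestyle and logistic models have no list from which clinic could be missing. Even so, a covariate that is not named in advance becomes a choice made after the data are seen.

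**Conclusion.** The omission is real and worth correcting: clinic is named in neither covariate list, and nothing elsewhere in the plan takes its place. The consequence is conditional on residual clinic differences in both meal timing and glycaemia, whose size is unknown. At ±0.2 SD the error barely moves. At ±0.3 SD it is about 6% to 8%, and at ±0.5 SD about 15% to 25%, depending on how far the clinic orderings agree.

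The 25% should not be read as the expected error rate. It needs 14.3% of the variance of both variables to lie between clinics, in the same order, after adjustment, and nothing in the documents supports that as the likely case. Nor do the documents show that any finding will be confounded. This is a low-severity improvement to the analysis.

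**What to change.** In Statistical Analysis, add clinic as a three-level fixed factor (two indicators) to the night-meal generalized linear model and the ANCOVA. Name it also for the lifestyle generalized linear model of the continuous glycaemic outcomes, which has no covariate list at present. With only three clinics, a fixed factor is more suitable than a random intercept. Keep the clinic code in the analysis dataset.

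The logistic regressions are outside this change, because two extra parameters cost more there if diabetes cases are few. A stratified or sensitivity analysis by clinic is an option for them.

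The cost is a phrase in the plan and 2 degrees of freedom. The change is cheap but not free: if meal timing itself differs by clinic, power falls from the planned 0.90 to the values in the last step of the working.

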Figure 1 Theoretical framework showed factors affecting circadian rhythm.

The investigator propose that the individual is nested within their environment which includes the influences of social demands e.g. social timing resulting from demands such as school or work schedules, social activities, family obligations and routines, parenting practices, community involvement, time zone, etc., the modern lighting and climate controlled environment, as well as the effect of the earth's natural environment. Within the individual, there is an interdependence of the circadian clocks, behavior, and health. The major contribution of this model is that the circannual clock interacts with the circadian clocks to promote optimal glucose tolerance of individual's circannual influences may have health consequences. The investigator propose interactions within the individual and across levels of this model. For example, social demands influence an individual's behavior which affects alignment of the clocks either by direct entrainment of the peripheral clocks (i.e., meal timing and consistency) or by affecting exposure to the light-dark cycle via sleep timing and consistency, physical activity, and exposure to artificial light at night. It is also proposed that circadian disruption caused by the environmental factors may contribute to disruption of circannual rhythms of growth, resulting in accelerated blood sugar and contributing to the development of type 2 diabetes mellitus.

[figure not shown]

Figure 2 Conceptual framework

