To investigate the association of physical activity (MET score and steps count), sedentary behaviors (MET score), sleep pattern (sleep duration), diet quality (distribution of total energy, carbohydrate, protein, and fat), and light exposure (timing responded to a different type of light) with glycemic outcome, the multivariable generalized linear model will be conducted. Meanwhile, anthropometric measures (body mass index, body fat, and waist circumference) will be categorized as either normal or overweight and obesity group, followed by using logistic regression to examine the association between anthropometry status and glycemic outcome (non-diabetes or diabetes). In addition, the glycemic outcome will be categorized into diabetes incidence (diabetes and non-diabetes) to determine the participants who had been diagnosed with diabetes at 6 months. A logistic regression test will be used to examine the association between early and late-night mealtime and diabetes incidence.

Quality control

To ensure that the database accurately reflects the data reported in the questionnaires, a pre-test will be carried out. The research assistant trained to conduct the study procedures included interviewing administrative questionnaires, CGMS device, 3 days dietary record, and pedometer. Monthly meetings are held with the principal

investigator to review study procedures and progression. A monthly report will be documented after the meeting.

Data monitoring and management

Participants are anonymized and assigned with a specific ID at study entry. To ensure accuracy and completeness of data entry, data are checked by identifying if there is any outlier or missing value. The data checking process is performed in the first, third and sixth month of the data collection, such that the experience gained can be used to train the research assistant for improvement. Paper documents are kept in a locked cabinet and electronic data are stored on password-protected computers which can only be accessed by research team members. All records will be kept for at least 5 years after completing the study. After 5 years, all papers will be shredded using an office shredder. Extra care should be taken with sensitive or confidential information and a secure paper destruction service bin used. Digital data will be destroyed by deleting or overwriting information and destroying the physical media, such as CD rom.

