APPENDIX H

Project Name:

Date of interview:

Pittsburgh Sleep Quality Index Questionnaire

Meal Timing and Glucose Tolerance

		/				/			
d	d		m	m	m		y	y	y

177

178

179

180

181

182

183

Pittsburgh Sleep Quality Index

183

184

185 Instructions: The following questions relate to your workday sleep habits over the past month
 186 only. You need to state the most accurate answer for most of the days and nights of the past
 187 month. **Please answer all questions.**

188

189 1. In the past month, what time did you usually go to bed at night on weekdays?

190

_____ a.m / p.m

191

192 2. In the past month, how many minutes did it usually take you to fall asleep each night on a
 193 weekday? _____ minutes

194

195 3. In the past month, what time do you usually get up in the morning on
 196 weekdays? _____ a.m

197

198 4. In the past month, how many hours did you get actual sleep at night on weekdays? (This
 199 may be different from the number of hours you lie in bed).

200

_____ hours

201

202 Instructions: The following questions relate to your sleep habits on rest days during the past
 203 month only. You need to state the most accurate answer for most of the days and nights of the
 204 past month. **Please answer all questions.**

205

206 5. In the past month, what time do you usually sleep at night on rest days?

207

_____ a.m / p.m

208

209 6. In the past month, how many minutes did it usually take you to fall asleep each night on a
 210 day off? _____ minutes

211

212 7. In the past month, what time do you usually get up in the morning on a day
 213 off? _____ a.m

214

215 8. In the past month, how many hours did you get actual sleep at night on a day off? (This may
 216 be different from the number of hours you lie in bed). _____ hours

217

218

219

220

221

222 Instructions: The following questions relate to your normal sleep habits over the past month
 223 only. You need to state the most accurate answer for most of the days and nights of the past
 224 month. **Please answer all questions.**

225

226 9. In the past month, how often did you have trouble sleeping because you (Please tick ✓
227 on the appropriate answer)

228

229 a. Can't sleep in 30 minutes
230 No for last month
231 Less than once a week
232 Once or twice a week

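### The ANCOVA adjusts sleep timing and chronotype for light exposure and sleep pattern, which can remove part of the association under test, and no planned model would show it.

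*Combined protocol and SAP*

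**What the plan says.** The hypothesis in Section 3 names two exposures, morning chronotype and early meal timing. In the Statistical Analysis part, the ANCOVA takes six exposures. Breakfast skipping and meal frequency come first, followed by "eating window, sleep timing, chronotype, and fasting pattern". All six get one covariate list: "controlling for potential covariates (sociodemographic characteristics, light exposure, diet quality, physical activity and sleep pattern").

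The covariates of interest are described elsewhere:

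- **Light exposure.** The next paragraph of the Statistical Analysis, for a different model, gives "light exposure (timing responded to a different type of light"). The instrument in Appendix G is an hourly grid with five light-source codes and one for darkness. The analysed variable is to be categorical, but the categories are not given.
- **Sleep pattern.** The ANCOVA sentence does not define it. Study Outcomes takes it from the Pittsburgh index, which asks (Appendix H) "what time did you usually go to bed at night on weekdays", with matching items on rising times and rest days. The paragraph after the ANCOVA, for its own model, reduces sleep pattern to sleep duration.
- **Framework.** Section 1, in the text before Figure 2, describes behaviour as "affecting exposure to the light-dark cycle via sleep timing and consistency".

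No unadjusted or total-association model and no exposure-specific covariate set is described. The plan does not say whether the six exposures share one model.

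**The concern.** If a covariate lies on the path from exposure to outcome, or measures the exposure a second time, adjusting for it takes away part of what is being estimated. Both are possible here. On the plan's own framework, light-dark exposure follows from sleep timing, and an hourly light grid with a darkness code can track when a person sleeps. The Pittsburgh bed and rise times are the same kind of clock times as those in the chronotype questionnaire (Appendix D) and the Chrononutrition Profile (Appendix I).

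Chronotype is half of the stated hypothesis. With only the fully adjusted ANCOVA, a null result for chronotype or sleep timing would have two readings, no association or an association adjusted away, and nothing planned would separate them.

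**Working it through.** **1. Reproduce the plan's figure.** Sample size Calculation gives "Statistical Test: Linear Multiple Regression Fixed Model, single regression coefficient", "Effect Size (β -coefficient): 0.13", two tails, "α Error prob: 0.05" and power 0.90. Use the noncentral t with noncentrality √(N·f²) and df = N − predictors − 1. With 0.13 entered as Cohen's f², N = 83 (power 0.9007 with one predictor). With 1 to 20 predictors N stays at 83 or 84. Dropout: 83/(1 − 0.5) = 166. Both figures reproduce. The number 83 is obtained only with 0.13 as f²; as a standardised slope it would need 614. The sizing makes no allowance for correlation between exposure and covariates.

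**2. Imprecision alone.** Let R² be the share of the exposure explained by light exposure and sleep pattern. The documents give no value, so it is varied. Holding the slope fixed and letting the covariates explain no further outcome variance, f² becomes 0.13 × (1 − R²) and the standard error grows by 1/√(1 − R²).

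| Assumed R² | Adjusted f² | SE factor | Power at N = 83 |
|---|---|---|---|
| 0 | 0.130 | 1.00 | 0.90 |
| 0.10 | 0.117 | 1.05 | 0.87 |
| 0.25 | 0.0975 | 1.15 | 0.80 |
| 0.50 | 0.065 | 1.41 | 0.63 |
| 0.70 | 0.039 | 1.83 | 0.43 |

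**3. Mediation added.** The total standardised slope is b = √(0.13/1.13) = 0.339. If a fraction m passes through the covariate, the direct slope is d = (1 − m)b, the covariate's slope is c = mb/√R², and f² = d²(1 − R²)/(1 − d² − c² − 2dc√R²). At R² = 0.25:

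- m = 0.25: f² = 0.0562, power 0.57
- m = 0.50: f² = 0.0270, power 0.32
- m = 0.75: f² = 0.0078, power 0.13

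With m = 0 at the same overlap, power is 0.80. The fraction m is also an assumption.

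**4. Sleep pattern as clock times.** If the covariate is an equally good second measure of the exposure, correlated ρ with it, the adjusted coefficient is 1/(1 + ρ) of the unadjusted one. At ρ = 0.5 it keeps 67% (power 0.48); at ρ = 0.7 it keeps 59% (power 0.28). It never falls below half.

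**5. Sleep pattern as duration only.** Take mid-sleep as the timing exposure, with onset SD 1, wake SD s and onset-wake correlation r. The covariance of mid-sleep and duration is (s² − 1)/2, their variances are (1 + s² + 2rs)/4 and 1 + s² − 2rs, and R² is the squared covariance over the product of the variances. It is 0 when s = 1, and about 0.05 to 0.25 for s of 0.8, 1.25 or 1.5 with r from 0.3 to 0.7 (assumed). Most of the exposure is then untouched by this covariate.

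**The case against.** A reader might infer that the ANCOVA removes most of what it tests, or that it turns a true association into a null finding. The documents support neither.

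- **No overlap is given.** At 10% or 25%, which nothing in the plan rules out, power is still 0.87 or 0.80.
- **Sleep pattern may not repeat the exposure.** The only explicit definition in the analysis section is duration, which need not correlate with timing. Using the Pittsburgh clock times as covariates is possible but not stated.
- **The light categories are unspecified.** Nothing says that the darkness hours form the analysed variable, so how closely it tracks sleep is unknown.
- **The direction is not settled.** Section 2, heading 3.2, has chronotype arising partly from the pacemaker's response to light, which is a reason to adjust. The Section 1 sentence does not mention chronotype, and it lists artificial light at night beside sleep timing.
- **The power baseline is borrowed.** The sizing concerns chrononutrition, with an effect from a late-dinner cohort. Chronotype is categorical, so with more than two groups a one-degree-of-freedom calculation is only a guide.

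All of this stands and limits the size of the claim. It does not remove the point. The plan's two accounts of light call for different models, and only one is planned. For the four meal-related exposures, sleep and light are plausible confounders, and the planned adjustment is reasonable.

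**Conclusion.** The concern holds as a risk of over-adjustment for two of the six exposures, with the loss unquantified. The plan adjusts sleep timing and chronotype for a timing-based light variable that its own framework can place downstream of sleep timing, and for a sleep variable left undefined in that model. Some of the association may be removed, and the planned output could not show it.

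The power range of about 87% to 43% at 83 participants rests on assumed overlaps of 10% to 70%, on 0.13 as f², on a single coefficient, and on covariates that explain no further outcome variance. It reflects imprecision only; any mediation comes on top. If sleep pattern is duration only, light exposure is the main remaining source of the problem.

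**What to change.** For the sleep-timing and chronotype terms only, fit and report two models side by side:

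1. The planned covariates, including sociodemographics, diet quality and physical activity, without light exposure and sleep pattern. Label this the total association.
2. The same model with light exposure and sleep pattern added. Label this the association not passing through them.

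Define sleep pattern in model 2 as sleep duration, as the neighbouring model already does, and do not use the Pittsburgh bed or rise times as covariates for these two exposures. Keep the planned covariates for the meal-timing exposures.

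This is a cheap improvement: SAP wording and extra model fits for each glycaemic outcome (HbA1c, FPG, 2-hour glucose, CGM), with no new data. The downside is that, if light is upstream of chronotype, confounding by light is controlled only in model 2. Both models must therefore be reported, and neither read alone.
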